### **8.2.1.1 Initial Tumor Imaging**

Initial tumor scans at Screening must be performed within 28 days prior to the date of allocation. Any scans obtained after Cycle 1 Day 1 cannot be included in the screening assessment. The site must review screening scans to confirm the participant has measurable disease per RECIST 1.1. The site study team must submit screening scans to the iCRO to confirm the participant has measurable disease per RECIST 1.1 prior to allocation. Tumor scans at Screening includes CT (preferred) or MRI of the abdomen and pelvis and CT of the chest. See the SIM for additional details.

### **8.2.1.2 Tumor Imaging During the Study**

The first on-study scan should be performed at 12 weeks (84 days  $\pm$ 7 days) from the date of allocation. Subsequent tumor scans should be performed every 12 weeks (84 days  $\pm$ 7 days) or more frequently if clinically indicated. After 54 weeks (378 days  $\pm$ 7 days), participants who remain on treatment will have scans performed every 24 weeks (168 days  $\pm$ 7 days). Scan timing should follow calendar days and should not be adjusted for delays in cycle starts. Scans are to be performed until disease progression is identified by the investigator or notification by the Sponsor, or until the start of new anticancer treatment, withdrawal of consent, or death, whichever occurs first.

Objective response should be confirmed by a repeat scan performed at least 4 weeks after the first indication of a response is observed. Participants will then return to the regular scan schedule, starting with the next scheduled time point. Participants who receive additional scans for confirmation do not need to undergo the next scheduled scan if it is fewer than 4 weeks later; scans may resume at the subsequent scheduled time point.

On-study brain or bone scans should be performed if clinically indicated or to confirm CR (if other lesions indicate CR and brain or bone lesions existed at baseline).

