Poststudy Anticancer Therapy						X	X	X	All anticancer therapy will be recorded until time of death or termination of Survival Follow-up. If a clinic visit is not feasible, follow-up information may be obtained via telephone or e-mail.

Study Period	Screening Phase	Intervention Phase (Q3W)			End of Treatment	Post-treatment Follow-up			Notes
		1	2	3 and onwards		Safety Follow-up a	Follow-up b	Survival Follow-up	
Treatment Cycle					Discontinuation				Procedures should occur predose on Day 1 of each cycle unless otherwise noted.  Post-treatment Period: Refer to Section 8.12.3.
Scheduled Timing	-28 to -1				At time of d/c	30 days post last dose		~Q12W (telephone)	
Window (days):		+ 3	± 3	± 3		+ 7	± 7	± 7	
Survival Status		<----->						X	After investigator-determined PD or start of new anticancer treatment. In addition, upon Sponsor request, participants may be contacted for survival status at any time during the course of the study (unless this information is not allowed to be provided due to confidentiality).
Efficacy Procedures									
Tumor Imaging (CT/MRI; Chest, Abdomen, and Pelvis)	X	<-----> c			X d			X	Prior scans performed within the screening period but before signing informed consent may be used if consistent with protocol requirements per SIM. All imaging visits have a scheduling window of ±7 days. Imaging to be performed Q12W or sooner if clinically indicated from the date of C1D1 until Week 54 of study treatment, Q24W or sooner if clinically indicated thereafter, or more frequently if required by local standard of care until disease progression per RECIST 1.1.

Study Period	Screening Phase	Intervention Phase (Q3W)			End of Treatment	Post-treatment Follow-up			Notes
		1	2	3 and onwards		Safety Follow-up a	Follow-up b	Survival Follow-up	
Treatment Cycle					Discontinuation				Procedures should occur predose on Day 1 of each cycle unless otherwise noted.  Post-treatment Period: Refer to Section 8.12.3.
Scheduled Timing	-28 to -1				At time of d/c	30 days post last dose		~Q12W (telephone)	
Window (days):		+ 3	± 3	± 3		+ 7	± 7	± 7	
Safety Procedures									
Height	X	X	X	X	X				Pediatric height to be measured at every visit. Adult height measured at Screening only.
Weight	X	X	X	X	X				To be measured at every visit.
Full Physical Examination	X								Within 7 days prior to C1D1.

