### **4.2.1 Rationale for Endpoints**

#### **4.2.1.1 Efficacy Endpoints**

This study will use ORR, defined as the proportion of participants who have best response as CR or PR. Responses are based on RECIST 1.1 criteria as assessed by blinded independent central review (BICR) as the primary endpoint. Objective response rate (ORR) is an acceptable measure of clinical benefit for a late stage study that demonstrates superiority of a new antineoplastic therapy, especially if the magnitude of the effect is large and the therapy has an acceptable risk/benefit profile. The use of BICR and RECIST 1.1 to assess ORR is

typically considered acceptable by regulatory authorities. Images will be submitted to an imaging CRO (iCRO) and read by independent central review blinded to treatment assignment to minimize bias in the response assessments.

Secondary efficacy endpoints include DOR, PFS, and OS.

Duration of response (DOR) as assessed by BICR per RECIST 1.1 criteria is a commonly accepted endpoint by both regulatory authorities and the oncology community to assess durability of responses to oncology treatments.

In this study, PFS is to be assessed by BICR per RECIST 1.1 criteria. The use of BICR and RECIST 1.1 to assess PFS is typically considered acceptable by regulatory authorities. Images will be submitted to an iCRO and read by independent central review blinded to treatment assignment to minimize bias in the response assessments. In addition, the final determination of radiologic progression will be based on the central assessment of progression, rather than a local site investigator/radiology assessment.

Overall survival (OS) is the gold standard for a “hard endpoint” in clinical studies in the area of oncology.

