### **8.2 Efficacy Assessments**

#### **8.2.1 Tumor Imaging and Assessment of Disease**

Throughout this section, the term 'scan' refers to any medical imaging data used to assess tumor burden and may include cross-sectional imaging (such as CT or MRI), medical photography, or other methods as specified in this protocol.

In addition to survival, efficacy will be assessed based on evaluation of scan changes in tumor burden over time, until the participant is discontinued from the study or goes into Survival Follow-up. The process for scan collection and transmission to the iCRO can be found in the Site Imaging Manual (SIM). Tumor scans by CT are strongly preferred. For the abdomen and pelvis, contrast-enhanced MRI may be used when CT with iodinated contrast is contraindicated, or when mandated by local practice. The same scan technique should be used in a participant throughout the study to optimize the reproducibility of the assessment of existing and new tumor burden and improve the accuracy of the response assessment based on scans.

Note: for the purposes of assessing tumor scans, the term “investigator” refers to the local investigator at the site and/or the radiological reviewer at the site or at an offsite facility.

In general, scans should include the chest, abdomen, and pelvis.

Expedited confirmation of measurable disease based on RECIST 1.1 by BICR at Screening will be used to determine participant eligibility. Confirmation by the BICR that the participant's imaging shows at least 1 lesion that is appropriate for selection as a target lesion per RECIST 1.1 is required prior to participant allocation.

All scheduled imaging for all study participants will be submitted to the iCRO. In addition, imaging that is obtained at an unscheduled time point for any reason (including suspicion of progression or other clinical reason) should also be submitted to the iCRO if it shows progression, or if it is used to support a response assessment. All imaging acquired within the protocol-specified window of time around a scheduled imaging visit can be classified as pertaining to that visit. Photographs of cutaneous lesions do not need to be submitted to the iCRO.

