### **8.2.1.3 End-of-Treatment and Follow-up Tumor Imaging**

For participants who discontinue study intervention, tumor imaging should be performed at the time of treatment discontinuation ( $\pm$ 4 week window). If previous imaging was obtained

within 4 weeks prior to the date of discontinuation, then imaging at treatment discontinuation is not mandatory. For participants who discontinue study intervention due to confirmed disease progression, this is the final required tumor imaging if the investigator elects not to implement iRECIST.

For participants who discontinue study intervention without confirmed disease progression, every effort should be made to continue monitoring disease status by tumor imaging using the same imaging schedule used while on treatment (Q12W until Week 54 after C1D1 [ $\pm 7$  days], Q24W thereafter or sooner or more frequently if required by local standard of care, until disease progression per RECIST 1.1) until the start of a new anticancer treatment, disease progression, pregnancy, death, withdrawal of consent, or the end of the study, whichever occurs first.

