#### **8.2.1.4 RECIST 1.1 Assessment of Disease**

RECIST 1.1 will be used by BICR as the primary measure for assessment of tumor response, date of disease progression, and as a basis for all protocol guidelines related to disease status (eg, discontinuation of study intervention). Although RECIST 1.1 references a maximum of 5 target lesions in total and 2 per organ, this protocol allows a maximum of 10 target lesions in total and 5 per organ, if clinically relevant to enable a broader sampling of tumor burden.

[Figure 2](#) illustrates the imaging flow involving verification of PD for clinically stable participants.

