#### **8.2.1.5 iRECIST Assessment of Disease**

iRECIST is based on RECIST 1.1, but adapted to account for the unique tumor response seen with immunotherapeutic drugs. iRECIST will be used by the investigator to assess tumor response and progression, and make treatment decisions. When clinically stable, participants should not be discontinued until progression is confirmed by the investigator, working with local radiology, according to the rules outlined in Appendix 8. This allowance to continue treatment despite initial radiologic PD takes into account the observation that some participants can have a transient tumor flare in the first few months after the start of immunotherapy, and then experience subsequent disease response. This data will be captured in the clinical database.

Clinical stability is defined as the following:

- Absence of symptoms and signs indicating clinically significant progression of disease
- No decline in ECOG performance status (or Lansky scale, if appropriate)
- No requirements for intensified management, including increased analgesia, radiation, or other palliative care

Any participant deemed clinically unstable should be discontinued from study intervention at site-assessed first radiologic evidence of PD, and is not required to have repeat tumor imaging for confirmation of PD by iRECIST.

If the investigator decides to continue treatment, the participant may continue to receive study intervention and the tumor assessment should be repeated 4 to 8 weeks later to confirm PD by iRECIST, per investigator assessment. Images should continue to be sent in to the iCRO for potential retrospective BICR.

If repeat imaging does not confirm PD per iRECIST, as assessed by the investigator, and the participant continues to be clinically stable, study intervention may continue and follow the regular imaging schedule. If PD is confirmed, participants will be discontinued from study intervention.

If a participant has confirmed radiographic progression (iCPD) as defined in Appendix 8, study intervention should be discontinued; however, if the participant is achieving a clinically meaningful benefit, an exception to continue study intervention may be considered following consultation with the Sponsor. In this case, if study intervention is continued, tumor imaging should continue to be performed following the intervals as outlined in Section 8 and submitted to the iCRO.

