### 9.6.1.3 Progression-free Survival

The non-parametric Kaplan-Meier method will be used to estimate the PFS survival curve. 95% CIs for the median PFS and PFS point estimates at various follow-up times from the first day of study treatment will be calculated.

Since disease progression is assessed periodically, PD can occur any time in the time interval between the last assessment where PD was not documented and the assessment when PD is documented. The true date of disease progression will be approximated by the earlier of the date of the first assessment at which PD is objectively documented per RECIST 1.1 by BICR and the date of death. Death is always considered a PD event. Participants who do not

experience a PFS event will be censored at the last disease assessment. The censoring rules for the analysis of PFS are summarized in [Table 9](#). If a participant meets multiple criteria for censoring, the censoring criterion that occurs earliest will be applied.

Table 9 Censoring Rules for Analysis of PFS

Situation	Date of Progression or Censoring
PD or death documented after $\leq 1$ missed disease assessment, and before new anticancer therapy, if any	Progressed at date of documented PD or death
PD or death documented immediately after $\geq 2$ consecutive missed disease assessments or after new anticancer therapy, if any	Censored at last disease assessment prior to the earlier date of $\geq 2$ consecutive missed disease assessment and new anticancer therapy, if any
No PD and no death; and new anticancer treatment is not initiated	Censored at last disease assessment
No PD and no death; new anticancer treatment is initiated	Censored at last disease assessment before new anticancer treatment
PD=progressive disease; PFS=progression-free survival	

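### Scanning can stop on the investigator's progression call while PFS and DOR count only central-review progression or death, and Section 9 neither tests nor counts the resulting censoring

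*Combined protocol and SAP*

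**What the plan says.** **When imaging ends.** Section 8.2.1.2 states: "Scans are to be performed until disease progression is identified by the investigator or notification by the Sponsor". New anticancer treatment, withdrawal of consent and death also end scanning. Section 8.2.1 has scan-based efficacy assessed "until the participant is discontinued from the study or goes into Survival Follow-up". The survival-status row of the Schedule of Activities (Section 1.3) is timed "After investigator-determined PD or start of new anticancer treatment". That row triggers a contact and is not itself an imaging stop.

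**What counts as an event.** Section 4.2.1.1 says "the final determination of radiologic progression will be based on the central assessment of progression, rather than a local site investigator/radiology assessment". Sections 9.4.1.2 and 9.6.1.3 define PFS on BICR progression or death, and DOR is likewise based on BICR.

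**How the rest are censored.** Without a BICR event, Tables 8 and 9 censor at the last assessment. If new therapy has started, the Table 9 entry is "Censored at last disease assessment before new anticancer treatment". A BICR progression or death after new therapy, or immediately after two or more consecutive missed assessments, is also censored.

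**What else is planned.** Section 3 lists exploratory investigator iRECIST PFS and DOR, with methods left to the supplemental SAP (Section 9.6). Section 9 gives one censoring scheme for each endpoint. It contains no sensitivity analysis for this censoring and no investigator/BICR discordance summary.

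**The concern.** Kaplan-Meier estimation assumes that a censored participant has the same future risk as those still followed. A participant whose site has just called progression probably does not. If BICR reads the same scan as not progressed and no further scan is taken, the participant leaves the risk set as event-free when the next scan might have been a BICR event. PFS and DOR then read too high.

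The exposed group is fairly narrow. It is mainly participants who start new therapy, and those who are clinically unstable at first site progression. Under Section 8.2.1.5 an unstable participant "should be discontinued from study intervention at site-assessed first radiologic evidence of PD, and is not required to have repeat tumor imaging" to confirm progression by iRECIST.

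Section 4.2 rests support for the postmarketing requirement on a robust ORR and durable responses by BICR, and DOR is the measure of durability. A single-arm study has no control arm in which the same bias could cancel.

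**Working it through.** **1. Whose call ends imaging.**
- Section 8.2.1.2 names the investigator.
- Section 1.2 (footnotes), Section 1.3 (imaging row and footnote b), Section 8.2.1.3 and Section 8.12.3.2 refer to progression per RECIST 1.1 without naming an assessor.
- Section 8.2.1.4 has BICR use RECIST 1.1 "as a basis for all protocol guidelines related to disease status (eg, discontinuation of study intervention").
- Section 8.12.3.3 ties Survival Follow-up to confirmed progression or new therapy.
- Section 8.2.1.3 says: "For participants who discontinue study intervention without confirmed disease progression, every effort should be made to continue monitoring disease status by tumor imaging". The Synopsis, Section 1.2 footnote d, Section 4.1 and Section 8.12.3.2 provide follow-up imaging only for those who stop for reasons other than progression. A participant stopped for unconfirmed site progression is covered by the first rule but not by the others.
- Expedited BICR is described only for measurable disease at screening (Sections 8.2.1 and 8.2.1.1). After site progression, images go to the imaging vendor for possible retrospective review.

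**2. The plan's own figures.** Section 9.9 gives precision for ORR only. Exact Clopper-Pearson limits for 28/50 are 41.3% and 70.0%, and for 24/50 they are 33.7% and 62.6%, as printed in Table 11. The plan gives no figure for PFS, DOR or discordance.

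**3. Inputs.** From the earlier pembrolizumab study in Section 2.2.1.3: 24-month PFS S = 0.48, and 28 responders with 20 ongoing. Assumed:
- d = share of progressions called by the investigator only: 10% or 20%
- r = share of these recovered by repeat scans: 0 or 0.5
- q = share of PFS events that are deaths, which cannot be discordant: 0 or 0.2

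**4. PFS.** If a constant fraction f = d(1−r)(1−q) of events becomes censorings, Kaplan-Meier estimates approximately S^(1−f).

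| r | q | d = 10% | d = 20% |
|---|---|---|---|
| 0 | 0 | 0.48^0.90 = 51.7% | 0.48^0.80 = 55.6% |
| 0.5 | 0 | 0.48^0.95 = 49.8% | 0.48^0.90 = 51.7% |
| 0 | 0.2 | 0.48^0.92 = 50.9% | 0.48^0.84 = 54.0% |
| 0.5 | 0.2 | 0.48^0.96 = 49.4% | 0.48^0.92 = 50.9% |

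A simulation (400,000 participants, exponential PFS, recovered cases dated about 6 weeks later) gave 51.6% and 55.5% for the first row, 50.0% and 51.9% for the second, and 50.9% and 53.9% for the third.

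**5. Check on the scan schedule.** A discrete model used scans at Weeks 12, 24, 36, 48, 72 and 96, anchored at PFS of 52% (Week 48) and 48% (Week 96). It compared the plan with continued scanning in which BICR calls progression at the next scheduled scan. Two assumed event-time shapes, early-weighted and flatter, gave an upward bias of 3.2 to 4.0 points at d = 10% and 6.6 to 8.1 points at d = 20%. These lean high because deaths and repeat scans are ignored. At 48% PFS, 50 participants give 50 × 0.52 = 26 events, so 2.6 or 5.2 would be investigator-only. With continued scanning the curve reached 50% by Week 96 in both shapes. At d = 10% under the plan it did not, so the median can change from reached to not reached.

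**6. DOR (crude).** 28 − 20 = 8, so at most 8 responses had ended. 8 × 0.1 = 0.8 and 8 × 0.2 = 1.6 events. 20/28 = 71.4% would read at most 0.714^0.9 = 73.9% or 0.714^0.8 = 76.4%.

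**7. The opposite case.** Suppose BICR would never have called progression and the extra site calls are independent, at d times the event hazard. In simulation the main analysis then read 48.1% and 48.0%, about unbiased. An analysis counting those calls as events read 44.7% and 41.4%, which is too low.

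**The case against.** The strongest reply is that the group is small and the figures are assumed. All scheduled imaging goes to the imaging vendor, as do unscheduled scans that show progression, so BICR sees the scan on which the site acted and only a true disagreement between readers is at issue. Stable participants who continue treatment are rescanned at 4 to 8 weeks. Section 8.2.1.3 can be read as keeping unstable participants on the scan schedule, since their progression is unconfirmed. Deaths before new therapy remain events if no more than one assessment was missed. With both mitigations in the formula the shift is 1 to 3 points, against a 95% interval of 33.7% to 62.6% for an observed 48% in 50 participants (Table 11). For DOR, the exact interval for 20/28 is about 51% to 87%. There is no hypothesis to overturn, and the remedy can err downward by as much as the bias it addresses.

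Most of this stands as a limit on size. It does not remove the problem. Sending the scan to BICR does not resolve a disagreement between readers, and the imaging rule relied on is undercut by the other sections. The bias runs in one direction and adds to the sampling error that the interval describes. Exploratory iRECIST analyses apply different progression rules and, as described, are not a sensitivity analysis of the BICR RECIST 1.1 censoring. The supplemental SAP is not available and may add something, but Section 9.6 sends only exploratory methods there.

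**Conclusion.** The concern holds. The protocol permits imaging to stop on an investigator call, the analysis recognises only BICR progression or death, and Section 9 neither tests nor counts the censoring that follows.

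The size is unknown. Under the assumed 10% to 20% discordance, 24-month PFS would be overstated by about 4 to 8 points at most in the formula, and by about 1 to 3 points with both mitigations. DOR would change by about 1 to 2 events. These figures need the further assumption that BICR would have called progression on later scans; otherwise the main estimate is about right. Only secondary, descriptive endpoints are affected, but DOR carries the durability claim. The point is worth fixing and does not threaten the primary analysis.

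**What to change.** 1. In Sections 9.6.1.2 and 9.6.1.3, prespecify one sensitivity analysis of PFS and DOR. In it, investigator RECIST 1.1 progression, or the start of new anticancer therapy, without prior BICR progression counts as an event on that date. Label it a conservative lower bound, because it may bias downward. Report the number of such participants beside the main estimate.
2. Reconcile Sections 1.2, 1.3, 8.2.1.2 to 8.2.1.5 and 8.12.3.2 on whose RECIST 1.1 call ends imaging, and align the Synopsis and Section 4.1 on who receives follow-up imaging.

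Item 1 costs SAP wording and one extra analysis. The data are already collected: investigator assessments under Section 8.2.1.5 and anticancer therapy under Section 6.5. Section 9 promises a protocol amendment for changes to methods for key secondary objectives, and Table 10 places DOR, PFS and OS under that heading, so an amendment may be needed. The sponsor also accepts a companion figure that may be less favourable. Item 2 is wording only. Neither item asks for a new central verification process.
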